**Table 5: Event and Censoring Details for Time to First flare/relapse after initial CDA**

Situation	Date of First flare/relapse or Date of Censoring	Censored/ Event
No assessments after first CDA	Date of first CDA	Censored
Flare/relapse before Week 37	Date of first relapse	Event

Situation	Date of First flare/relapse or Date of Censoring	Censored/Event
Rituximab administered	Date of first Rituximab administration	Censored
No flare/relapse during the Blinded Treatment Period	Date of last efficacy assessment during blinded treatment phase (through Week 37)	Censored
Study discontinuation	Date of last efficacy assessment prior to or on the date of treatment discontinuation	Censored
Death before flare/relapse	Date of death	Censored

- Note: Patients will be censored prior to a flare/relapse event should a censoring reason occur. Censoring reasons may be categorized for reporting (e.g. by discontinuation reason). A patient must have a CDA in order to be included in this analysis.
- Complete remission for  $\geq 8$  weeks on zero CS at Week 61 = Yes if complete remission status is achieved at Weeks 53, 57, and 61 with no recorded CS usage during this time; No otherwise, provided all data is complete for the specified visits. For patients with missing data at the specified visits this endpoint value will be missing unless there are a documented CR both before and after the missing visit.
- TEAE = any adverse event with an onset date on or after the first dose of study drug, having been absent pre-treatment or worsening relative to pre-treatment state.
- TEAE (Blinded Treatment Period) = any TEAE with an onset date on or after the first dose of study drug and occurring before enrollment into the open-label portion of the study. TEAEs that are ongoing at the time of enrollment into the open-label portion are considered part of the double-blind portion of the study.
- TEAE (Open-Label Extension Period) = any TEAE with an onset date on or after enrollment into the open-label extension portion of the study, having been absent during the double-blind portion or worsening relative to double-blind portion state. Since the TEAE time is not collected for the study, any AE started or worsened on the first day of the open-label period is considered a TEAE for the blinded treatment period.

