- TEAE (Long Term Extension Period) = any TEAE with an onset date on or after enrollment into the long term extension portion of the study, having been absent during the double-blind/open-label extension portion or worsening relative to double-blind/open-label extension portion state. Since the TEAE time is not collected for the study, any AE

started or worsened on the first day of the long term extension period is considered a TEAE for the open-label extension period.

- Treatment duration (days) =

$$\text{Date of last dose of study drug} - \text{Date of first dose of study drug} + 1$$

For subjects who are missing the date of last study drug application, the last visit date will be used in the calculation of treatment duration.

- Study Drug Compliance (%) =

$$\left( \frac{\text{Total number of tablets taken during the treatment}}{\text{Total number of tablets planned during the treatment}} \right) \times 100\%$$

The total number of tablets taken will be calculated by subtracting the number of tablets returned from the number of tablets dispensed. The total number of tablets planned will be calculated by multiplying the total number of days of planned exposure to study drug by 2.

- Corticosteroid compliance (%) = amount (mg) of systemic corticosteroid prescription doses taken divided by amount (mg) of corticosteroid expected to be taken, as collected on the “Prednisone/Prednisolone Accountability” eCRF form.

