## 9.1. Adverse Events

All AEs, TEAEs, and SAEs will be coded using the MedDRA dictionary version 24.0.

A TEAE is defined as any AE with an onset date/time on or after the first dose of study drug, having been absent pre-treatment or worsening relative to pre-treatment state. TEAEs will be broken down into Blinded Treatment Period TEAEs; Open-Label Extension Period TEAEs; and Long Term Extension TEAEs. A double-blind TEAE is defined as any TEAE with an onset date on or after the first dose of study drug and occurring before enrollment into the open-label portion of the study. TEAEs that are ongoing at the time of enrollment into the open-label portion are considered part of the double-blind portion of the study. An open-label TEAE is defined as any TEAE with an onset date on or after enrollment into the open-label portion of the study, having been absent during the double-blind portion or worsening relative to double-blind portion state. TEAEs for the long-term extension study will be determined similarly, based on the relative timing and severity of an event with respect to the end of the open-label period and start of the long term extension.

All summaries of TEAEs will be presented separately for the double-blind and open-label portions of the study for the Safety Population.

An overall summary of TEAEs will be presented including the total number of events, frequency counts, and percentages for:

- Any TEAEs
- Any treatment-related TEAEs
- Any TEAE leading to study discontinuation
- Any SAEs
- TEAEs resulting in death
- TEAEs by Grade (severity)
- Action Taken with Study Drug for all TEAEs (Study Drug Dose Not Changed, Study Drug Dose Interrupted, Study Drug Discontinued)
- TEAEs related to Corticosteroids

Summaries of the incidence of TEAEs and SAEs will be displayed by:

- SOC and PT
- SOC, PT, and maximum severity grade
- SOC, PT, and maximum causality (not related, related) to the study drug

In the case of multiple occurrences of the same TEAE within the same subject, each subject will only be counted once a preferred term. In the summaries showing severity and relationship to study medication the event with the maximum severity grade or strongest relationship (not related < related) will be reported. If an event is missing the severity, then severe will be used in the summary analyses (severity = severe); If an event is missing the relationship, then related

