will be assumed for summary analyses (relationship = related). These data imputations are for categorization purpose only and will not be used in listings.

All TEAEs summarized by system organ class (SOC) and preferred term (PT) will be sorted in order of descending frequency of the SOC and then by descending frequency order (total across treatment groups) of the PT within each SOC.

In addition, summaries of TEAEs will be displayed by:

- SOC, HLGT, HLT and PT

In the AE data listings, all AEs will be displayed. AEs that are not treatment-emergent will be flagged.

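### Read literally, the open-label TEAE definition leaves a resolved event that recurs at the same or a lower grade out of both the blinded and the open-label TEAE tables; for the long-term extension, SAP 6.1.8 and 9.1 set different references

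*SAP*

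**What the plan says.** SAP 6.1.8 (Derived Variables, in the list after Table 5) builds the definitions in layers.

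- **General:** "TEAE = any adverse event with an onset date on or after the first dose of study drug, having been absent pre-treatment", or worse than before treatment.
- **Blinded period:** a TEAE "occurring before enrollment into the open-label portion of the study".
- **Open-label extension (OLE):** a TEAE with onset at or after open-label enrolment, and also "having been absent during the double-blind portion or worsening relative to double-blind portion state". SAP 9.1 repeats this condition.
- **Long-term extension (LTE):** parallel wording in 6.1.8, "having been absent during the double-blind/open-label extension portion or worsening relative to double-blind/open-label extension portion state". SAP 9.1 describes the LTE differently, by the timing and "severity of an event with respect to the end of the open-label period and start of the long term extension".
- **First-day rule:** "any AE started or worsened on the first day of the open-label period is considered a TEAE for the blinded treatment period". The first LTE day is handled the same way.

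On reporting, SAP 9.1 states: "All summaries of TEAEs will be presented separately for the double-blind and open-label portions of the study for the Safety Population". Section 9 adds that the LTE is reported separately and that summaries are by double-blind treatment group and overall. No pooled whole-study TEAE table is specified. The listings show every AE, and "AEs that are not treatment-emergent will be flagged".

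**The concern.** The OLE condition looks back to presence at any time in the blinded period. It does not ask whether the event was still present when open-label treatment began. Take a placebo patient with Grade 1 nausea at Week 5 that resolves, and Grade 1 nausea again two weeks after the first rilzabrutinib dose. The second episode starts too late for the blinded table. It was not absent earlier and is no worse, so the open-label table excludes it as well.

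What is at stake is the open-label incidence of ordinary recurring events. Placebo patients take rilzabrutinib for the first time in the OLE (SAP 3.1), so the column for the former placebo group is where toxicity on first exposure should appear. The protocol (2.1 and 4.2) names long-term safety data as a purpose of both extensions.

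**Working it through.** The plan gives no figure to reproduce. The check is on the logic of the definitions, followed by an illustration of size.

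**1. Where the recurrence is placed.** Consider an event absent before treatment, with a first episode that starts and resolves in the blinded period, and a second episode of the same or lower grade starting after the first open-label day.

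| Rule | Second episode |
|---|---|
| General TEAE | Met: onset after first dose, absent before treatment |
| Blinded TEAE | Not met: starts after open-label enrolment |
| First-day rule | Does not apply |
| OLE TEAE, absence limb | Not met: present earlier in the blinded period |
| OLE TEAE, worsening limb, worst blinded grade as reference | Not met: grade no higher |
| OLE TEAE, worsening limb, state at end of blinded period as reference | Met: resolved to present is a worsening |

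The result turns on what *state* means, and the SAP does not define it.

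**2. Counting grade combinations.** Protocol 8.6.3.3 uses Grades 1 to 4, with death treated as an outcome. Let g1 be the grade of the first episode and g2 that of the recurrence, giving 4 × 4 = 16 pairs.

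- Whole-period reference: a pair is dropped when g2 ≤ g1, which is 1 + 2 + 3 + 4 = **10 of 16**. A pair is counted when g2 > g1, which is 3 + 2 + 1 + 0 = **6 of 16**.
- End-of-period reference: **0 of 16** are dropped.

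These are combinations, not expected frequencies.

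**3. The LTE.** The 6.1.8 wording looks back over the blinded and open-label periods, 36 + 24 = 60 weeks. The 9.1 wording refers to the end of the OLE and the start of the LTE. A Grade 1 event that resolved before the LTE and recurs in it at Grade 1 is excluded under the first and counted under the second.

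**4. Illustration of size, on assumed inputs.** Let pb be the share of patients who had the term in the blinded period, RR the relative risk of an open-label event given an earlier one, 15% the open-label incidence in patients without an earlier event, and 75% the share of recurrences that are no worse. Then

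- incidence = 0.15 × [(1 − pb) + pb × RR]
- lost = 0.15 × pb × RR × 0.75

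| pb | RR | Incidence | Lost | Share lost | Of 60 patients |
|---|---|---|---|---|---|
| 0.15 | 1 | 0.150 | 0.017 | 11% | 1 of 9 |
| 0.15 | 2 | 0.173 | 0.034 | 20% | 2 of 10 |
| 0.30 | 1 | 0.150 | 0.034 | 23% | 2 of 9 |
| 0.30 | 2 | 0.195 | 0.068 | 35% | 4 of 12 |

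Only the figure of about 60 placebo patients comes from the documents (Protocol 4.1). The table also assumes that all of them enter the OLE and that every earlier episode had resolved. The Phase 2 rates in Protocol 2.2.4 (nausea 15%, headache 11%) are drug-related events on rilzabrutinib, so they do not supply pb for patients on placebo.

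**The case against.** The best defence is that *state* can mean the state at the end of the blinded period, in which case nothing is lost. Two features of the SAP lean that way: the first-day rules turn on when an AE started or worsened, and the partial-date rule in 6.1.11 allocates an AE by the period in which it started. This is a possible reading, but it makes the absence limb redundant, because anything absent throughout the blinded period is also absent at its end. SAP 9.1 repeats the OLE condition without clarifying it. Two programmers could follow the same sentence and produce different tables.

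The defence is right that much stays visible. The first episode remains in the blinded table. SAEs are tabulated (9.1.3), deaths are listed, AEs leading to withdrawal are listed (9.1.2), and so are all AEs. The placebo-controlled comparison is untouched, and no safety tests are planned. SAP 4.3 allows data from before and after a target visit to be combined, but its example is exposure and it promises no pooled AE table. Listings do not give incidence, and the SAE tables do not cover non-serious recurrences.

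A reader might infer more than the text supports:

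- **That every recurrence is dropped.** A recurrence at a higher grade counts in the OLE, and one on the first open-label day goes to the blinded period.
- **That the LTE exclusion is settled, so understatement grows with exposure and rates appear to fall.** This holds only under 6.1.8; the reference in 9.1 would count the recurrence.
- **That the listings will flag these recurrences as not treatment-emergent.** They still meet the general definition, so the flag need not apply.

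**Conclusion.** The gap is real for the OLE under the plain reading of 6.1.8 and 9.1. An event that resolved in the blinded period and recurs at the same or a lower grade after the first open-label day has no place in either period's TEAE table. Open-label incidence is understated as a result, with most consequence for placebo patients starting rilzabrutinib. For the LTE the finding is an inconsistency between 6.1.8 and 9.1, not an established exclusion.

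The documents do not fix the size. The 11% to 35% in the illustration follows from assumed rates and should not be quoted as an estimate; under an end-of-period reading the loss is zero. This should be corrected before the safety tables are programmed. It does not bear on efficacy or on the blinded safety comparison.

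**What to change.** In SAP 6.1.8 and 9.1, define an OLE or LTE TEAE as any event that meets the general TEAE definition and either

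- has a new onset in that period, including recurrence after resolution, or
- was ongoing at the end of the preceding period and worsens in the new one.

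Use the state at the end of the preceding period as the reference for both extensions, so that 6.1.8 and 9.1 agree on the LTE. Keep the general condition (absent before treatment, or worse than then). Without it, a pre-treatment complaint that returns unchanged would count in the extensions but not in the blinded period. Keep the first-day rule. Because 6.1.11 plans no imputation of resolution dates, add one line on how an earlier episode with no end date is treated.

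The cost is a few sentences and one programming rule, with no new data. The downside is that open-label and LTE rates become slightly less favourable.

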##### 6.1.1.1 Packaging

PRN1008 (Rilzabrutinib) drug product or placebo will be supplied to the clinical sites in blister cards. Each blister card will contain 14 tablets of rilzabrutinib or placebo with day and night designation to provide guidance to the subject on which tablet to ingest. Subjects will receive rilzabrutinib or placebo tablets in a kit containing 5 blister cards or 5-week supply of rilzabrutinib or placebo (70 tablets).

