### **Dispensing of CS and rilzabrutinib/placebo in Suvoda:**

1. Corticosteroids may be dispensed at any time using Corticosteroid Dispensing Visit Transaction in the IWRS. Reference page 17 of IWRS Site User Manual to dispense additional CS.

Complete the paper Drug Accountability Log with corticosteroids dispensed.

2. Rilzabrutinib/placebo may only be dispensed at a regular scheduled visit. Select the next scheduled patient visit. Respond "Yes" when asked if the visit was performed. A kit will be dispensed. If you select "No", the visit will be skipped and no kit will be dispensed. If the visit occurs outside the protocol specified window, you will be prompted to confirm that you would like to continue with registering the visit out of window. Respond "Yes."

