## 7.4. Exposure and Compliance

The following parameters will be summarized by treatment group for the safety population, and for blinded treatment period and open-label extension period:

- Treatment exposure
- Study drug compliance
- Corticosteroid compliance
- Number of times that CS was not returned during blinded and open-label periods,

Study exposure will also be summarized for long term extension period.

For subjects who are missing the date of last study drug administration, for any reason, the last study visit date will be used in the calculation of treatment duration, and exposure will be calculated up to that date. Study drug compliance will not be calculated for those subjects whose date of last study drug administration is unknown. The number and percentage of patients with compliance between 80% and 125% will be tabulated for both study drug and CS.

The compliance for CS is based on systemic prescription doses collected on “Prednisone/Prenisoline Accountability” eCRF form. CS doses collected as concomitant medications on “Other Corticosteroid Concomitant Medications” eCRF form are not included in the compliance calculations.

For the blinded period, CS doses collected from Day 1 until Week 37 Visit (until early termination visit for patients prematurely discontinued study prior to Week 37 visit) are included in the derivation. For open label extension period, CS doses collected from beginning of open label extension period until Week 61 Visit (until early termination visit for patients prematurely discontinued study during the open label extension period) are included in the derivation. For long term extension period, CS doses collected from beginning of long term extension period until Week 109 Visit (until early termination visit for patients prematurely discontinued study during the open label extension period) are included in the derivation.

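### The study-drug compliance formula scores unreturned tablets as swallowed, which biases the compliance table upwards

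*SAP*

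**What the plan says.** **Formula (SAP 6.1.8, Study Drug Compliance).** Compliance is tablets taken over tablets planned, as a percentage. For the numerator: "The total number of tablets taken will be calculated by subtracting the number of tablets returned from the number of tablets dispensed". For the denominator: "The total number of tablets planned will be calculated by multiplying the total number of days of planned exposure to study drug by 2". There is no rule for study drug that is neither returned nor otherwise accounted for, and planned exposure is not defined.

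**Reporting (SAP 7.4).** "The number and percentage of patients with compliance between 80% and 125% will be tabulated for both study drug and CS". The same section lists, for corticosteroid only, "Number of times that CS was not returned during blinded and open-label periods"; study drug has no matching item. The one stated reason for leaving study-drug compliance uncalculated is an unknown date of last dose.

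**Supply (Protocol 6.1.1.1 and Appendix 9A).** "Each blister card will contain 14 tablets of rilzabrutinib or placebo", and patients are supplied "in a kit containing 5 blister cards or 5-week supply of rilzabrutinib or placebo (70 tablets". For a performed scheduled visit, the dispensing instructions in Appendix 9A say "A kit will be dispensed". Protocol Table 2 schedules blinded dispensing at Day 1 and then every four weeks from Week 5 to Week 33; the Week 37 supply is open-label (footnote p).

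**Returns (Protocol 6.2.3).** Patients have to hand back everything, emptied or not, at each visit.

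**The concern.** A returned tablet cannot have been swallowed, but an unreturned one may or may not have been. Dispensed minus returned is therefore an upper bound on intake, and it equals intake only when every unused tablet comes back. The SAP treats the bound as the value.

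The kit size makes this matter more than usual. Each kit carries 70/56 = 125% of what its interval needs, and the tabulated band also ends at 125%. A completer with no returns at all can land at the top edge of the band, indistinguishable in the table from a patient who took nearly every dose.

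At stake is how far the compliance table can be relied on when a reader asks whether a small or absent effect might reflect drug not taken. Protocol 6.4 bases compliance on dispensing records and medication counts, so a rule that turns poor accountability into apparent intake weakens that table.

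**Working it through.** **Inputs**

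- Tablets per kit: 5 × 14 = 70. At two a day, 70/14 = 5 weeks, which reproduces the protocol's stated supply.
- Blinded dispensing visits: Day 1 and Weeks 5, 9, 13, 17, 21, 25, 29, 33 = 9. One kit at each (taken from Appendix 9A) gives 9 × 70 = 630 tablets.
- Planned tablets: 36 weeks = 252 days, so 504. Counting to nominal Day 253 (SAP Table 2) gives 506. Counting doses from Day 1 to the morning of Day 253 gives 505.

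**Completer who returns nothing**

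| Planned tablets | Score |
|---|---|
| 504 | 630/504 = 125.0% |
| 505 | 630/505 = 124.8% |
| 506 | 630/506 = 124.5% |

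The score is the same whether 0, 252 or 504 tablets were swallowed. By comparison, a fully adherent completer who returns all 125 leftovers scores (630 − 125)/504 = 100.2%. To fall below 80%, a completer must return at least 227 tablets: (630 − 227)/504 = 79.96%.

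The open-label period behaves the same way. Six kits (Weeks 37, 41, 45, 49, 53, 57) hold 420 tablets: 420/336 = 125.0%, or 420/338 = 124.3%.

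**Partial non-return**

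Let f be true adherence and k the number of kits not returned, with all other leftovers returned. Then

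score = (70k + 56f(9 − k))/504.

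| True adherence | Kits unreturned | Score |
|---|---|---|
| 50% | 4 of 9 | (280 + 140)/504 = 83.3% |
| 60% | 3 of 9 | (210 + 201.6)/504 = 81.7% |
| 70% | 2 of 9 | (140 + 274.4)/504 = 82.2% |

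Each unreturned kit adds (70 − 56f)/504: 8.3 percentage points at f = 0.5 and 2.8 points at f = 1. These cases do not depend on how the 125% boundary is read.

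**Where the completer figure does not apply**

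- *Visit window.* If planned days follow the patient's own dates, the ±3-day window at Week 37 covers roughly 249 to 256 days, and a zero-return score runs from 630/498 = 126.5% down to 630/512 = 123.0%. At 251 days or fewer it is above the band.
- *Early discontinuation.* A zero-return patient stopping at Day 30 has two kits. On own duration the score is 140/60 = 233%; on a fixed 504 it is 140/504 = 27.8%. Either falls outside the band.
- *Missed or extra dispensing.* One missed kit gives 560/504 = 111.1%, still inside. An additional kit would push the score above 125%.

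**The case against.** The strongest reply is that this is one descriptive table with other safeguards around it.

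- The SAP defines no per-protocol set, and no efficacy analysis uses study-drug compliance. Treatment duration comes from dose dates, which this formula does not touch. This stands, and it limits the point to the compliance table.
- Non-return departs from the protocol's return rule, and SAP 7.2 lists all deviations. That makes it traceable, but a listing does not alter the score.
- There is other evidence on intake. PK samples are taken through the blinded period with the times of the last two doses recorded. At remote visits the site must ask how many tablets remain and confirm compliance (Appendix 9A), and patients are to bring medication to the next clinic visit. So a reader who infers that the pill count is the trial's only evidence of intake goes too far. The SAP formula makes no use of these remaining-tablet counts, however.
- Compliance is not calculated when the last-dose date is unknown, which removes some likely non-returners. Those with a known date stay in.
- The partial cases need two to four of nine kits missing, and the documents give no non-return frequency. This also stands: the direction of the bias is certain, its size in this trial is not.

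A reader might also infer that every non-returner is labelled compliant, or that 125% can never be exceeded. Neither is supported. The SAP tabulates a band without naming it, does not say whether its ends are included, and the window, early-stop and extra-dispensing cases can all fall outside it.

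**Conclusion.** The point holds for the compliance table and no further. Under the stated formula, unreturned study drug counts as intake, so the score can only be at or above the true value. For a completer near the nominal schedule with no returns, the score is about 124.5–125% regardless of intake. With two to four of nine kits unreturned, adherence of 50–70% is reported as 82–83%.

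This rests on one 70-tablet kit at each of nine blinded visits, and, for the 125.0% case only, on reading the band as inclusive. The total bias cannot be estimated from the documents. The primary result, the key secondary results and the dose-date exposure summary are unaffected.

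**What to change.** In SAP 6.1.8 and 7.4:

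1. Do not count tablets from an unreturned kit as taken.
2. Report compliance as not evaluable for patients with unreturned kits, and give a sensitivity bound that counts those kits as zero taken. For the patient with 50% adherence and four missing kits, the bound is 140/504 = 27.8%; the current rule gives 83.3%, so the two figures bracket the truth.
3. Tabulate unreturned study-drug kits by arm, as is already done for corticosteroid. A kit brought back late should count as returned.
4. Define planned exposure (fixed period or the patient's own dates) and say whether 125% is inside the band.

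The band itself need not be narrowed; the documents give no basis for another upper limit. The SAP already has an uncalculated category for unknown last-dose dates, so item 2 extends existing practice. The cost is one derivation change and one extra table row, assuming returns are recorded by kit, which the documents do not show for study drug. Some patients lose a compliance value, and the reported figure may look slightly less favourable.
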